•	Change in 12-lead ECG variables (HR, PR, QRS, QT, QTcB, and QTcF) from pre-dose to selected post-doses assessments (1 h, 2 h, 3 h, 4 h) on Day 1 and on day of re-initiation of study drug;
•	Notable abnormalities for selected 12-lead ECG parameters (HR, PR, QT, QTcF) at 3-h post-dose assessment on Day 1, Week 12 and at the re-initiation of study drug when post-dose monitoring is required.
•	Treatment-emergent decrease of forced expiratory volume in 1 second (FEV ₁) or forced vital capacity (FVC) $> 20\%$ from baseline values;
•	Treatment-emergent decrease of percent predicted FEV_1 or $FVC > 20$ percentage points from baseline values;
•	Change in FEV ₁ or FVC from baseline, absolute and % of absolute change to all timepoints up to EOS;
•	Change from baseline to EOS vs change from baseline to EOT in FEV_1 or FVC (absolute and % of predicted);
•	Among subjects with a decrease of ≥ 200 mL or $\geq 12\%$ in FEV ₁ or FVC from baseline to EOT, reversibility defined as a decrease of < 200 mL and < 12% in FEV ₁ or FVC from baseline to last available FU;
•	Change in lung diffusion capacity as assessed by the diffusing capacity of the lung for carbon monoxide (DL _{CO} ; at selected sites only), expressed in absolute change and $\%$ of predicted value from baseline to all timepoints up to EOS;
•	Change from baseline to EOS vs change from baseline to EOT in DLco (absolute and % of predicted) (at selected sites only);
•	Treatment-emergent notable blood pressure abnormalities;
•	Treatment-emergent notable laboratory abnormalities;
•	Change in body weight from baseline to EOS;

5 December 2018, page 40/376

	• Treatment-emergent electronic Columbia-Suicide Severity Rating Scale (eC-SSRS) suicidal ideation score of 4 or above, or a "yes" response on the eC-SSRS suicidal behavior item.							
	 Quality of life endpoints Change from baseline by visit up to Week 108 in SF-36v2[™] Health Survey domain and component scores. 							
	 Pharmacoeconomic endpoints Change from baseline by visit up to Week 108 in work productivity and activity impairment in MS (WPAI:MS) scores. 							
	• Health care resource utilization from baseline up to Week 108 (number of hospitalizations, length of stay, number of intensive care admissions for MS relapse and visits to an emergency medical services facility for MS).							
	Pharmacokinetic (PK) endpoints							
	• Plasma concentrations of ponesimod pre-dose at Week 12 Week 60 and Week 108 and 3 h post-dose on Day 1 and at Week 12.							

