- (4) The symptoms scale (with a 24-h recall) will be completed for 7 consecutive days (the day of the visit and the 6 days after the visit). During pre-randomization, subjects during Visit 1 (Screening) will be provided with the FSIQ-RMS and will be instructed to complete the symptoms domain (i.e., section 1) of the FSIQ-RMS on 7 consecutive days prior to randomization at home (provided no other assessment performed in the meantime exclude the subject). Once the results from the laboratory tests confirm the subject's eligibility, the site coordinator will contact the subject to instruct him/her to start the completion of the FSIQ-RMS at latest 7 days before the randomization.
- (5) No CGI-C assessment at Baseline.
- (6) Health care resource utilization data, including number of intensive care unit admission for MS relapses and emergency medical services facility visits for MS
- (7) Only for subjects participating in the patient preference substudy. The Multiple Sclerosis Patient Preference Questionnaire will be completed at home twice during pre-randomization (after Visits 1 and 2 [Screening and Baseline]).
- (8) Any CXR that has been performed within 90 days prior to screening can be used (in this case, no need to repeat CXR at Screening). In case of re-screening, CXR does not need to be repeated if CXR was performed within 90 days prior to the date of re-screening.
- (9) Brain MRI to be performed at any time an opportunistic infection in the central nervous system is suspected. In addition, non-conventional MRI techniques (MTR and DIR) will be performed at selected sites only.
- (10) Dermatological examination to be performed by a dermatologist. In case of re-screening, skin examination does not need to be repeated if skin examination from initial screening was performed within 90 days prior to the date of re-screening
- (11) Height only at Visit 1 (Screening).
- (12) SBP/DBP: Pre-dose and hourly (+/- 15 min) for at least 4 h post-dose and up to 12 h.

(13) Only pre-dose ECGs at all visits except Day 1 and Week 12.

(14) Pre-dose and hourly (+/-15 min) for at least 4 h post-dose and up to 12 h.

- (15) Pre-dose and 3-h(+/-15 min) post-dose ECGs.
- (16) OCT and/or ophthalmological examination to be performed at any visit in the presence of visual symptoms or findings suggestive of macular edema or active uveitis [see Section 5.1.13.7].

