1.3.2.4 Safety and tolerability

Clinical studies to date have identified transient changes in heart rate (HR) and atrioventricular (AV) conduction as the most prominent safety-related signal with ponesimod. Oral doses of ponesimod resulted in dose-dependent sinus rate reductions in all treated subjects; the changes were transient and resolved largely within 6–10 h after dosing. In some subjects, these HR reductions were accompanied by a transient effect on AV conduction with prolongation of the PR interval on the electrocardiogram (ECG) and, occasionally, second degree AV-block. The effects on HR and AV conduction diminish with repeated administration of ponesimod, indicating desensitization. To minimize the first-dose effects on HR and AV conduction, a dose up-titration regimen was successfully tested and is implemented in current clinical trials.

Difficulty in inspiration (dyspnea) and related pulmonary function test (PFT) changes have also been detected in humans. Mild transient dyspnea/cough was noted frequently 2–6 h after an oral dose of 40 mg or higher, and was associated with a clinically relevant forced expiratory volume in 1 second (FEV₁) decrease from baseline. Symptoms resolved spontaneously upon discontinuation of treatment with ponesimod, and PFTs returned to baseline upon drug discontinuation. Data from an interim analysis of the long-term extension study AC-058B201/B202 with a cut-off date of 31 October 2013 showed that dose-dependent decrease in FEV₁ remained stable in patients treated with ponesimod for a median of more than 3 years and remains reversible over the long term.

Elevations of aspartate transaminase (AST) and/or alanine aminotransferase (ALT) without any bilirubin increase have been noted with ponesimod; they have been reversible upon discontinuation of dosing. The changes were asymptomatic.

Individual cases of macular edema associated with changes in visual acuity have been observed in subjects treated with ponesimod. These events resolved upon discontinuation of ponesimod.

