At the time of discharge from cardiac monitoring (i.e., when the evaluation of the pre-dose and all the hourly post-dose ECGs until 4 h post-dose have been obtained) on Day 1, and on the first day of re-initiation of study drug following drug interruptions, the following criteria must be met:

- ECG-derived resting HR > 45 bpm, and if HR < 50 bpm it must not be the lowest value post-dose;
- SBP > 90 mmHg;
- QTcF < 500 ms and QTcF increase from pre-dose < 60ms;

• No persisting significant ECG abnormality (e.g., AV block second- or third-degree) or ongoing AE requiring continued cardiac monitoring or prohibiting study continuation as an out-patient.

If the subject does not meet the discharge criteria (as described above) at 4 h post-dose, the subject should be carefully monitored for an additional period, and a 12-lead ECG and a BP measurement must be performed every hour. The subject can be discharged from cardiac monitoring as soon as the above criteria are met.

Should the subject not meet the criteria for discharge from cardiac monitoring at 12 h postdose, she/he must be permanently discontinued from study drug. Subjects who are permanently discontinued should not be discharged from cardiac monitoring before vital signs return to near baseline values or until there is no persisting ECG abnormality (e.g., AV block second degree or higher), ongoing AE requiring continued cardiac monitoring, or until medically indicated.

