6.2 Safety endpoints

Treatment-emergent period is defined as the time from first study drug intake up to 15 days (inclusive) after last study drug intake. The following safety endpoints will be analyzed:

Treatment-emergent AEs, SAEs, AEs of special interest[#], and MACE

5 December 2018, page 121/376

- AEs leading to premature discontinuation of study treatment •
- Treatment-emergent morphological ECGs abnormalities (as defined by the ECG • provider)
- Change in 12-lead ECG variables (HR, PR, QRS, QT, QTcB, QTcF) from pre-dose to • selected post-dose assessments (1h, 2h, 3h, 4h) on Day 1 and on day of re-initiation of study drug
- Notable abnormalities* for selected 12-lead ECG variables (HR, PR, QT, QTcF) at • 3-hpost-dose assessment on Day 1, Week 12, and at the re-initiation of study drug when post-dose monitoring is required
- Treatment-emergent decrease of FEV_1 or FVC > 20% from baseline values
- Treatment-emergent decrease of percent predicted FEV_1 or FVC > 20 percentage • points from baseline values
- Change in FEV₁ or FVC from baseline, absolute and % of absolute change to all • timepoints up to EOS
- Change from baseline to EOS vs change from baseline to EOT in FEV_1 or FVC • (absolute and % of predicted)
- Among subjects with a decrease of $\geq 200 \text{ mL}$ or $\geq 12\%$ in FEV₁ or FVC from baseline • to EOT, reversibility defined as a decrease of < 200 mL and < 12% in FEV₁ or FVC from baseline to last available FU
- Change in lung diffusion capacity as assessed by DL_{CO} (at selected sites only), • expressed in absolute change and % of predicted value from baseline to all timepoints up to EOS
- Change from baseline to EOS vs change from baseline to EOT in DLco (absolute and • % of predicted; at selected sites only)
- Treatment-emergent notable BP abnormalities* •
- Treatment-emergent notable laboratory abnormalities* •
- Change in body weight from baseline to EOS •
- Treatment-emergent electronic self-rated version of the Columbia-Suicide Severity • Rating Scale (eC-SSRS) suicidal ideation score of 4 or above, or a "yes" response on the eC-SSRS suicidal behavior item

[#] The selection of AEs of special interest is based on the anticipated risks of treatment with ponesimod or teriflunomide (e.g., liver enzyme abnormalities) and on the events that may be related to MS comorbidities (e.g., seizures or stroke) as described in Appendix 5; the final list of AEs of special interest will be defined in the Statistical Analysis Plan (SAP).

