At Visit 3 pre-dose (Day 1), the first-dose administrator must provide the ECG results and interpretation to the principal investigator / treating neurologist and support her/him, if requested, to make a final decision on the subject's eligibility according to the inclusion/exclusion criteria. At Visit 3 (Day 1), the pre-dose ECG must be performed prior to randomization and the applicable points from exclusion criterion #18 (e.g., HR < 50 bpm, presence of second-degree AV block Mobitz Type II or third-degree AV block, or a QTcF interval > 470 ms (females), > 450 ms (males), see Section 4.4) must be ruled out.

During the treatment period ECGs must be performed at pre-dose. Additionally, at Visit 6 (Week 12) during the treatment period, ECGs must also be performed at 3 h post-dose. In case of need of concomitant treatment with a QT-prolonging drug with known risk of Torsades de Pointes, additional ECGs will be performed according to the guidance provided in Appendix 3.

At Visit 3 (Day 1) and on the day of re-initiation of study drug when post-dose monitoring is required [see Section 5.1.10], ECGs must be performed at pre-dose, and hourly (+/- 15 min) thereafter for a minimum of 4 h and up to 12 h post-dose. Subjects may be discharged from the cardiac monitoring if they meet the discharge criteria before 12 h post-dose but no sooner than the (report of) ECG at 4 h post-dose has been evaluated by the first-dose administrator [see Section 5.1.11]. If the subject does not meet the defined discharge criteria at 12 h post-dose, the subject will be permanently discontinued from the study drug but will continue to be monitored, and additional ECG measurements will be performed until changes in ECG variables are no longer clinically relevant [i.e., discharge criteria are met; see Section 5.1.11], or until medically indicated.

On Day 1 and on the first day of re-initiation of study drug when post-dose monitoring is required, significant findings, which in view of the first-dose administrator meet the definition of a (non-serious) AE, have an onset after the study drug intake, and are resolved at the time of discharge of the subject from cardiac monitoring, must be recorded directly on the AE page of the eCRF by the first-dose administrator. These AEs will not be visible

Ponesimod / ACT-128800 Relapsing multiple sclerosis Protocol AC-058B301, OPTIMUM Version 7 5 December 2018, page 135/376

Confidential

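### On Day 1 and at re-initiation, the only visible endpoint that counts notable HR and PR abnormalities reads the 3-h ECG alone; an any-hour HR and PR count should be added

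*Protocol*

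**What the plan says.** The synopsis lists, among the safety endpoints, "Notable abnormalities for selected 12-lead ECG parameters (HR, PR, QT, QTcF) at 3-h post-dose assessment on Day 1, Week 12" and at re-initiation when post-dose monitoring is required. Section 6.2 has the same restriction: "3-hpost-dose assessment on Day 1, Week 12, and at the re-initiation of study drug".

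The recording schedule is wider. Section 7.3.1 states that on Day 1 and on re-initiation days "ECGs must be performed at pre-dose, and hourly (+/- 15 min) thereafter for a minimum of 4 h and up to 12 h post-dose". Under Section 5.1.11, a subject who does not meet the discharge criteria at 4 h stays under observation and "a 12-lead ECG and a BP measurement must be performed every hour". At Week 12 the schedule is narrower; note 15 to Table 1 asks for "Pre-dose and 3-h(+/-15 min) post-dose ECGs".

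The companion quantitative endpoint covers change from pre-dose at "selected post-doses assessments (1 h, 2 h, 3 h, 4 h) on Day 1 and on day of re-initiation of study drug". Section 6.2 also lists treatment-emergent morphological ECG abnormalities, adverse events, and notable blood pressure and laboratory abnormalities, none tied to an hour. Its footnote leaves the final list of notable abnormalities to the SAP and points to Appendix 6.

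**The concern.** Section 1.3.2.4 presents transient change in heart rate and AV conduction as the leading safety signal of ponesimod and says that "the changes were transient and resolved largely within 6–10 h after dosing". An effect lasting that long is not confined to hour 3. The discharge rule in Section 5.1.11 asks whether an HR below 50 bpm is the lowest reading since dosing, so the protocol itself allows the lowest hour to differ between subjects.

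The endpoint that turns these ECGs into a number of affected subjects nevertheless looks at one hour. A subject whose HR or PR is beyond the limit at 2 h but acceptable at 3 h is counted as having no notable abnormality in it. Readings after 4 h exist mainly because discharge criteria were not met at 4 h, so they come from the subjects of most interest, and neither this endpoint nor the change endpoint uses them.

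At stake is the reported frequency of first-dose HR and PR outliers. The shortfall would be expected mainly in the ponesimod arm, since Section 5.1.3.1 gives teriflunomide subjects a mock up-titration, but the documents give no data on this.

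**Working it through.** The protocol states no figure to reproduce. The check compares the endpoint with the schedule and with the other safety outputs.

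**Step 1: share of ECGs used.** On Day 1 and re-initiation days there are 4 to 12 scheduled hourly post-dose ECGs (Section 7.3.1), and the endpoint uses one. 1/4 = 25%; 1/12 = 8.3%. At Week 12 it uses the only post-dose ECG taken, so no reading is lost there.

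**Step 2: what the other outputs cover on Day 1 and at re-initiation.**

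| Output | Hours | Counts subjects beyond an HR or PR limit? |
|---|---|---|
| Notable ECG abnormalities (6.2) | 3 h only | Yes |
| Change from pre-dose (6.2) | 1–4 h | No, change only |
| Morphological abnormalities (6.2) | No limit | No numeric HR or PR limit stated |
| Adverse events (6.2, 3.3.4) | No limit | Only if judged to be an adverse event |
| QTc > 450, > 480, > 500 ms (Version 7 rationale) | None stated | QTc only |

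Notable blood pressure abnormalities, measured on the same hourly schedule (Section 7.3.2), carry no hour limit. No reason is given for treating HR and PR differently.

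**Step 3: direction.** Every subject counted at 3 h is also counted at any hour. So P(abnormal at 3 h) ≤ P(abnormal at any hour), whatever the rates.

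**Step 4: illustration of size, on assumed values.** The documents give no hourly abnormality rates. Assume the same probability p at each of hours 1–4 and 550 ponesimod subjects (the planned arm size).

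- Independent hours: P(any) = 1 − (1 − p)^4. With p = 0.02: 1 − 0.98^4 = 0.0776.
- Correlated hours: P(any) = 1 − Φ4(c, c, c, c; ρ), where c is the 1 − p normal quantile, Φ4 is the four-variate normal distribution function and all pairs have correlation ρ.

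| p = 0.02 | P(any of 1–4 h) | Subjects of 550 | Ratio to 3-h count |
|---|---|---|---|
| 3 h only | 0.0200 | 11 | 1 |
| ρ = 0.9 | 0.0381 | 21 | 1.91 |
| ρ = 0.8 | 0.0466 | 26 | 2.33 |
| ρ = 0.5 | 0.0636 | 35 | 3.18 |
| Independent | 0.0776 | 43 | 3.88 |

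Over p = 0.01 to 0.05 the ratio runs from 1.76 (p = 0.05, ρ = 0.9) to 3.94 (p = 0.01, independent). It tends to 1 as the hours come to agree perfectly, and it is smaller if the effect peaks at 3 h. Hours 5–12 are not included.

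**The case against.** **Three hours is a coherent choice.** It is the only post-dose ECG at Week 12 and matches the 3-h PK samples on Day 1 and at Week 12. Every subject contributes one reading, so occasions can be compared. A most-extreme value to discharge draws on 4 readings in some subjects and up to 12 in others, and the number depends on the outcome. This stands, and it is why the 3-h endpoint should be kept.

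**The governing text is partly out of view.** Section 11.3.5.2 and Appendix 6 are not in the text at hand, and displays by timepoint are ordinary SAP content. This stands in part. The footnote to Section 6.2 defers the list of abnormalities, but the endpoint wording itself fixes the hour. If Section 11.3.5.2 already tabulates any-hour HR and PR outliers, only the endpoint wording needs aligning.

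**Other outputs catch the signal.** A reader might infer that first-dose bradycardia and QTcF extremes drop out of the safety analysis, or that a subject taken off drug for bradycardia would go unseen. The documents do not support that. The Version 7 amendment rationale describes treatment-emergent QTc thresholds with no hour limit, and Section 6.2 starts the treatment-emergent period at first intake. HR and PR changes are analysed at 1–4 h, AV block can enter as a morphological finding, and adverse events leading to discontinuation are an endpoint. What remains is the categorical count of HR and PR outliers.

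**Part of any gap is noise.** The lowest of four readings is lower than one reading even without a drug effect. In a simulation with assumed pre-dose HR of mean 70, SD 9 and floor 50 bpm, no drug effect and independent errors of SD 3–5 bpm, the 3-h reading captures only 34–36% of subjects with any HR below 50 in hours 1–4. An any-hour count must therefore be read against the other arm. This stands.

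**Conclusion.** The point holds for HR and PR outliers on Day 1 and at re-initiation. The synopsis and Section 6.2 both count them at one hour out of 4 to 12 recorded, and no other output visible in the protocol gives the number of subjects beyond an HR or PR limit at the remaining hours. It does not hold for Week 12 or for QTc.

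The direction is certain: the 3-h count can only equal or undercount the any-hour count. The size cannot be derived from the documents. It would be tempting to say that the 3-h reading misses a particular fraction of cases, but that fraction depends on the assumptions. With the assumed baseline above and mean HR falls of 3–8 bpm, the 3-h reading captured 48–67% of subjects with HR below 50 in hours 1–4 in one set of simulations. It captured 79–89% when the trough was placed at 3 h and hourly errors were correlated at 0.7. The baseline, the profile and the 50 bpm limit are all assumed.

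This concerns one descriptive safety endpoint. It has no bearing on the primary efficacy conclusion, and no data are lost.

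**What to change.** In Section 6.2 and the synopsis, keep the 3-h endpoint for comparison with Week 12 and the PK sample. Add the number and proportion of subjects, by arm, with a notable HR or PR abnormality at any post-dose ECG on Day 1 and on re-initiation days, shown in two ways:

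- hours 1–4, where the schedule is the same for all subjects;
- all hours to discharge, with the number of ECGs per subject alongside.

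Use the limits already set for notable abnormalities, and align the wording with Section 11.3.5.2 and Appendix 6. No assessment or clinical rule changes.

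The cost is endpoint wording and one more table, since Section 7.3.1 already has these ECGs recorded digitally and read centrally. The reported incidence will be higher in any arm where a crossing occurs only outside 3 h. The to-discharge count also rests on a number of readings that varies between subjects, so the hours 1–4 count should carry the comparison between arms.

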The endpoints "Time to first confirmed relapse" and "PCBV from baseline to Week 108" do not add substantial information on clinically important effects of the study drug on MS disease for the following reasons:

5 December 2018, page 23/376

- The endpoint "Time to first confirmed relapse" is highly correlated to the primary endpoint of ARR. Thus, although this endpoint may provide some additional insight into the drug's effect on relapse activity, it is not expected to add relevant information to what is already available through the primary endpoint of ARR.
- The clinical significance of brain volume loss in MS and the relevance of the endpoint "PCBV from baseline to Week 108" remains unclear as the degree of change in whole brain volume measurement that results in a clinically meaningful benefit is not well defined due to several methodological limitations in brain volume measurements.
- ii. Modify the multiple testing strategy for the control of the type I error by testing the secondary endpoints according to a fallback type method. As compared to the previously planned fixed-sequence hierarchical method, this will provide some opportunity to test an endpoint later in the sequence even if an endpoint tested earlier in the sequence has failed to show statistical significance. If statistical superiority of an endpoint tested earlier in the sequence can be shown the corresponding alpha can be passed on to endpoints later in the sequence. As a consequence, endpoints tested late in a fallback sequence are given a higher weight as compared to endpoints at the beginning of the sequence. This is in contrast to the previous planned hierarchical fixed sequence approach where endpoints at the beginning of the sequence receive a higher weight. To maintain the same weight ranking of the secondary endpoints it is proposed to change the order in the sequence.

The hypothesis for the primary endpoint of ARR is first tested with the full alpha. If the primary endpoint null hypothesis is rejected, the alpha will be split evenly (1/3 of alpha) between the following three secondary endpoints using the fallback procedure, allowing for passing on alpha as per the following sequence:

- Change from baseline to Week 108 in fatigue-related symptoms as measured by the symptoms domain of the FSIQ–RMS [Fatigue]
- Cumulative number of CUAL from baseline to Week 108 [CUALs]
- Time to 12-week CDA from baseline to EOS [12-week CDA]

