If a secondary endpoint listed as part of the fallback procedure above is successful, the preserved alpha is passed along to the next secondary endpoint in the sequence and the summed alpha is used for testing that endpoint. Thus, as sequential tests are successful, the alpha accumulates for the endpoints later in the sequence; these endpoints are then potentially tested with a progressively larger alpha, but always with at least 1/3 of the alpha.

In a last step, the secondary endpoint

• Time to 24-week CDA from baseline to EOS [24-week CDA]

is tested in a subsequent stage following Time to 12-week CDA with the remaining alpha.

A graphical description of this testing strategy for the primary and secondary endpoints following the approach from Bretz, et al. [Bretz 2009] is provided in Figure 8 Overall testing strategy.

Based on the latest published information from recent MS trials, the disability accumulation rate is expected to be lower than assumed in earlier protocol versions [Cohen 2018, Comi 2018]. This results in a lower than anticipated probability of the study providing a robust evaluation of the effect of ponesimod on disability accumulation and, consequently, would have limited the ability to assess the other secondary endpoints with the previously planned hierarchical multiple testing strategy. The sponsor considers that the introduced fallback type multiple testing strategy optimizes the ability of the trial to obtain conclusive results on key disease parameters.

Analyses for secondary endpoints will be conducted at an overall two-sided 5% alpha level, with multiplicity adjustment as per the above testing strategy. 95% confidence intervals will be presented. The statistical analyses sections and sample size calculations for the secondary endpoints have been updated accordingly.

Additional minor changes and clarifications were made to the protocol as follows:

- Cladribine was added to the list of orally administered disease-modifying therapies.
- It was clarified that oral taper of corticosteroids should not be administered in order to harmonize the treatment of relapses in the study and to minimize the risk of combined immunosuppression.
- It was clarified that No evidence of disease activity (NEDA) status will be considered up to EOS.
- It was corrected that health care utilization will be not be displayed by visit.

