The primary statistical analysis of the ARR endpoint will be performed on the FAS using a negative binomial model for confirmed relapses, with the stratification variables prior use of disease-modifying therapies (DMTs) and EDSS category as well as the number of relapses in the year prior to study entry, included in the model and time in the study as an offset variable. Sensitivity analyses will be performed on the PPS and also based on different subgroups derived from baseline variables.
The secondary efficacy endpoints will be tested if the primary analysis on ARR has led to the rejection of the null hypothesis in favor of ponesimod 20 mg at an overall two-sided significance level of 0.05. A fallback method will be used for testing the family of hypotheses related to the following three secondary endpoints:

5 December 2018, page 42/376

• Absolute change of FSIQ-RMS from baseline to Week 108.
• Cumulative number of CUAL from baseline to Week 108;
• Time to 12-week CDA from baseline up to EOS;
This is followed in a hierarchical manner by testing
• Time to 24-week CDA from baseline up to EOS;
at the remaining alpha.
The endpoints will be analyzed using the FAS population. All secondary endpoints will also be analyzed using the PPS population.
The sample size was calculated based on the primary endpoint, and power calculations are provided for the secondary endpoints.
Sample size for the primary endpoint
The sample size for the study was determined by a simulation using the negative binomial distribution. A sample size of 1100 subjects (550 per treatment group) would provide a power of approximately 90% for a significance level of 0.01, under the assumption that ARR is 0.320 for teriflunomide 14 mg and 0.215 for ponesimod 20 mg (which corresponds to a risk reduction of 33%) and using a dispersion = 0.9. An annual dropout rate of approximately 15% for the first year and 7.5% for the second year has been assumed.

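### As described, the secondary-endpoint testing procedure controls error at 5% but leaves alpha unused once 24-week CDA is rejected, so fatigue is never tested above 0.0167

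*Protocol*

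**What the plan says.** The strategy is set out in the rationale for Substantial Global Amendment 6 (item ii), which explains the rule that Version 7 introduces, and is repeated briefly in the synopsis under statistical methodology: "A fallback method will be used for testing the family of hypotheses related to the following three secondary endpoints".

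- Gatekeeper: "The hypothesis for the primary endpoint of ARR is first tested with the full alpha".
- Starting levels: if ARR is rejected, "the alpha will be split evenly (1/3 of alpha) between the following three secondary endpoints using the fallback procedure", in the order fatigue, CUAL, 12-week CDA.
- Transfer: after a success, "the preserved alpha is passed along to the next secondary endpoint in the sequence and the summed alpha is used for testing that endpoint". Each of the three is tested at a growing level, "but always with at least 1/3 of the alpha".
- Last step: 24-week CDA "is tested in a subsequent stage following Time to 12-week CDA with the remaining alpha".
- Overall level: the secondary analyses are "conducted at an overall two-sided 5% alpha level, with multiplicity adjustment as per the above testing strategy".
- Stated weighting: "endpoints tested late in a fallback sequence are given a higher weight as compared to endpoints at the beginning of the sequence". The order was changed with this in mind.

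The rationale refers to Figure 8 for a graph of the procedure, and Section 6.1.2 refers to Section 11.3.1. Neither was in the text available for this review.

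**The concern.** Fatigue is first in the sequence, so nothing precedes it to pass it alpha, and the text describes no path back. Its level is 0.0167 whatever happens elsewhere. Any fatigue p-value between 0.0167 and 0.05 remains non-significant even when the other three secondary endpoints have all succeeded and their alpha is free.

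The amendment presents the new strategy as a way to improve the trial's chance of conclusive results on key disease parameters, and it cites the graphical approach. In that approach an arrow out of the last hypothesis is allowed. A rule without one is dominated by the same rule with one. At stake is some power for fatigue, the patient-reported secondary endpoint. The validity of the trial is not at stake.

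**Working it through.** **Reproducing the plan's level.** 0.05/3 = 0.01667 for each of fatigue, CUAL and 12-week CDA; 3 × 0.01667 = 0.05. This agrees with the stated overall level.

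**The graph as the text reads.** Starting levels are 0.01667, 0.01667, 0.01667 and 0 for fatigue (F), CUAL (U), 12-week CDA (C12) and 24-week CDA (C24). Arrows F→U→C12→C24 each carry weight 1. Nothing leaves C24.

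**The graph with return arrows.** The same, plus C24→F and C24→U with weight 1/2 each.

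**Highest reachable levels**

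| Situation | As described | With return arrows |
|---|---|---|
| F, after U, C12 and C24 are rejected | 0.0167 | 0.05 |
| F and U both open, after C12 and C24 are rejected | 0.0167 each | 0.025 each |
| U, after F, C12 and C24 are rejected | 0.0333 | 0.05 |

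**Worked example (invented p-values).** F 0.02, U below 0.001, C12 0.01, C24 0.01. F fails at 0.0167. U passes at 0.0167, C12 at 0.0333 and C24 at 0.0333. As described, testing stops there and F is not significant. With return arrows F is retested at 0.0167 + 0.0333 = 0.05 and succeeds.

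**Error control.** Simulation of all 15 configurations with at least one true null (300,000 runs each; correlation between the CDA statistics 0 or 0.8) gives a maximum familywise error of 0.050 under both rules.

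| True nulls | As described | With return arrows |
|---|---|---|
| Fatigue only | 0.0168 | 0.0499 |
| Fatigue and CUAL | 0.033 | 0.049 |

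**Power.** The power inputs for the secondary endpoints (Section 11.5.2) were not visible, so all powers below are assumptions, stated as standalone two-sided power at 0.05. Fatigue's power at 0.01667 is Φ(1.960 + z − 2.394), where z is the normal quantile of its power at 0.05. For 80% this is Φ(1.960 + 0.842 − 2.394) = Φ(0.408) = 0.658; for 90% it is 0.802.

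If fatigue is independent of the rest, the gain is approximately

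gain ≈ P(0.0167 < p_F ≤ 0.05) × P(U ≤ 0.0167, C12 ≤ 0.0333, C24 ≤ 0.0333).

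With fatigue at 80% and CDA at 50/40%, this is 0.141 × 0.297 = 0.042.

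Full simulation (1,000,000 runs; CUAL 99%; CDA correlation 0.9, other endpoints independent; levels and gains rounded separately):

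| CDA power, 12-/24-week | Fatigue 80%: power, gain | Fatigue 90%: power, gain |
|---|---|---|
| 10/7% | 65.9 → 66.5, +0.6 | 80.2 → 80.6, +0.4 |
| 20/15% | 65.9 → 67.2, +1.3 | 80.2 → 81.2, +0.9 |
| 30/20% | 65.9 → 67.9, +1.9 | 80.2 → 81.6, +1.4 |
| 50/40% | 65.9 → 70.2, +4.2 | 80.2 → 83.2, +2.9 |
| 80/70% | 65.9 → 74.5, +8.5 | 80.2 → 86.2, +5.9 |

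CUAL gained at most 0.4 points, CDA power did not change, and no simulated trial lost a rejection.

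**Sensitivity.** With CDA correlation 0.8, all other correlations 0.2 and fatigue power 50 to 90%, the fatigue gains were 0.8 to 2.1 points (CDA 30/20%), 2.0 to 4.9 (50/40%) and 5.0 to 10.2 (80/70%). If CUAL power were only 60 to 90% (fatigue 80%, CDA 50/40%), CUAL would gain 0.5 to 1.3 points.

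**The case against.** The strongest reply is that the procedure is valid, that forward-only passing is what a fallback sequence ordinarily does, and that the protocol openly gives later endpoints more weight. Citing the graphical approach for a description does not commit the sponsor to an alpha-exhaustive graph. The amendment's immediate aim, that weak disability results should not block testing of fatigue and CUAL, is already met.

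Most of this stands as fact. The weighting argument does not justify the unused alpha, however. It explains the order, the equal starting split and the forward arrows, all of which would stay. Return arrows act only after both CDA endpoints have been rejected, so they cannot take anything from the endpoints the sponsor chose to favour.

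Two further objections stand and limit the point:

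- **Unseen material.** A reader might infer that the plan deliberately throws alpha away. The visible text is merely silent on what follows rejection of 24-week CDA, and Figure 8 and Section 11.3.1 may say more. Nor is alpha lost after the third fallback endpoint: it goes to 24-week CDA, and only what is left after that step is unused.
- **Size.** A reader might take the larger gains as typical. They need both CDA endpoints to succeed, and the amendment itself expects disability accumulation to be less frequent than earlier versions assumed. The low-power rows may therefore be the relevant ones.

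**Conclusion.** The point holds as one of efficiency. On the visible text the procedure controls familywise error at 5% but is not alpha-exhaustive, and fatigue is held at 0.0167 even when every other secondary endpoint succeeds. Return arrows improve on it at no cost to any other endpoint.

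Under the assumed powers (fatigue 80 to 90%, CUAL 99%), the loss for fatigue is about 0.5 to 2 points at low CDA power, 3 to 4 at medium and 6 to 9 at high. For CUAL it is at most 0.4 points, so CUAL is not a material part of the concern unless its power is well below 99%.

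It would be wrong to infer a type I error problem: the starting levels sum to 0.05 and the maximum simulated error is 0.050. It would also be wrong to call the low weight on fatigue an oversight, since the ranking is disclosed. The conclusion assumes that Figure 8 and Section 11.3.1 follow the prose.

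**What to change.** First check Figure 8 and Section 11.3.1.

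- If they contain no arrow out of 24-week CDA, add arrows from 24-week CDA to fatigue and to CUAL, for example with weight 1/2 each. Keep the 1/3 starting weights and the forward arrows. State in Section 11.3.1 and the synopsis that, once 24-week CDA is rejected, its alpha returns to whichever of fatigue and CUAL is still open, and that these are retested at the updated level by the usual graph-updating rule.
- If the return arrows already exist, change only the prose so that it describes them.

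The cost is two arrows and a sentence or two, and the testing program must follow the updated graph. Every rejection under the described rule is kept. The change must be fixed before unblinding; the amendment states that all data remain blinded to the sponsor, so it could be made then without knowledge of the results.
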